In addition, since statin exposure was increased by co-administration of ETC-1002, the time course of laboratory values such as CK, AST, ALT, or total bilirubin should be carefully monitored to confirm the presence or absence of muscle-related AE or AEs associated with hepatic impairment due to administration of statins, and if any abnormal

value is observed, appropriate measures including discontinuation of administration should be taken.

In the clinical trials conducted outside Japan, ETC-1002 was associated with AST and ALT increased, hemoglobin decreased, as well as creatinine and urea nitrogen increased, although these were not clinically significant. Therefore, changes in these laboratory test values should be carefully monitored, and appropriate measures should be taken if any abnormal value is observed.

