7.2 Demographic and Baseline Characteristics

For each analysis set, descriptive statistics (number of subjects, mean, standard deviation, median, minimum, and maximum; the same, hereinafter) of age, height, body weight, body mass index (BMI), and estimated glomerular filtration rate (eGFR), and frequency distributions of age groups (<65 years, ≥65 years and <75 years, ≥75 years), categorized BMI (<25 kg/m², ≥25 kg/m² and <30 kg/m², ≥30 kg/m²), categorized eGFR (<60 mL/min/1.73 m², ≥60 mL/min/1.73 m² and <90 mL/min/1.73 m², ≥90 mL/min/1.73 m²), sex, race, ethnicity, country, presence/absence of past medical history, and presence/absence of complications will be summarized by rollover, newly enrolled, and overall subjects.

The same analysis will be performed for each statin response.

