9.3 Clinical Laboratory Data

Among the urinalysis parameters in laboratory tests, those other than pH and specific gravity will be included in the qualitative urinalysis.

For parameters other than the qualitative urinalysis, descriptive statistics of the actual value and change from baseline will be calculated at each time point. For qualitative urinalysis parameters, shift tables at each time point from baseline will be prepared. For parameters other than qualitative urinalysis, measured values will be categorized using

the reference range to “below the lower limit of reference range,” “within the reference range,” and “above the upper limit of reference range,” and shift tables at each time point from baseline will be prepared.

The number and percentage of subjects meeting the criteria for identifying laboratory values of potential clinical relevance ([Appendix 2: Criteria for Identifying Laboratory Values of Potential Clinical Relevance](#)) and Hy’s law ([Appendix 7: Criteria for Hy’s Law](#)) after IMP administration will be calculated. All data obtained after IMP administration during the treatment period will be analyzed, including those obtained at unscheduled visits.

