Appendix 2 Criteria for Identifying Laboratory Values of Potential Clinical Relevance

Laboratory Tests	Criteria
Chemistry	
AST	$\geq 3 \times$ upper limit of normal (ULN)
ALT	$\geq 3 \times$ ULN
Bilirubin, Total	$\geq 2 \times$ ULN
ALP	$\geq 3 \times$ ULN
Urea nitrogen	≥ 30 mg/dL
Creatinine	≥ 2.0 mg/dL
Creatine kinase (CK)	$\geq 4 \times$ ULN
Uric acid	≥ 9 mg/dL
Hematology	
Hematocrit	Males: $\leq 37\%$ and ≥ 3 percentage points decrease from baseline Females: $\leq 32\%$ and ≥ 3 percentage points decrease from baseline
Hemoglobin	Males: ≤ 11.5 g/dL Females: ≤ 9.5 g/dL
Leukocyte count	$\leq 2,800 \times 10^6/L$
Leukocyte count	$\geq 16,000 \times 10^6/L$
Platelet count	$\leq 7.5 \times 10^{10}/L$
Platelet count	$\geq 70 \times 10^{10}/L$
Urinalysis	
Protein	Increase of ≥ 2 units
Glucose	Increase of ≥ 2 units
Additional criteria	
Chloride	≤ 90 mEq/L
Chloride	≥ 118 mEq/L
Potassium	≤ 2.5 mEq/L
Potassium	≥ 6.5 mEq/L
Sodium	≤ 126 mEq/L
Sodium	≥ 156 mEq/L
Calcium	≤ 8.2 mg/dL
Calcium	≥ 12 mg/dL
Glucose	Fasting: ≥ 126 mg/dL Non-Fasting: ≥ 200 mg/dL
Glucose	≤ 50 mg/dL
Total cholesterol	≥ 240 mg/dL
LDL cholesterol	≥ 160 mg/dL
HDL cholesterol	< 40 mg/dL
Triglycerides, Fasting	≥ 150 mg/dL

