Diabetes-related	10012601	Diabetes mellitus
Diabetes-related	10012607	Diabetes mellitus inadequate control
Diabetes-related	10012671	Diabetic ketoacidosis
Diabetes-related	10018429	Glucose tolerance impaired
Diabetes-related	10018478	Glucose urine present
Diabetes-related	10018473	Glycosuria

AE of Special Interest	PT Code	PT Term
Diabetes-related	10018484	Glycosylated haemoglobin increased
Diabetes-related	10020635	Hyperglycaemia
Diabetes-related	10056997	Impaired fasting glucose
Diabetes-related	10023379	Ketoacidosis
Diabetes-related	10023388	Ketonuria
Diabetes-related	10023391	Ketosis
Diabetes-related	10067585	Type 2 diabetes mellitus
Diabetes-related	10057597	Urine ketone body present
Renal dysfunction-related	10069339	Acute kidney injury
Renal dysfunction-related	10005481	Blood creatinine abnormal
Renal dysfunction-related	10005483	Blood creatinine increased
Renal dysfunction-related	10005846	Blood urea abnormal
Renal dysfunction-related	10005851	Blood urea increased
Renal dysfunction-related	10050760	Blood urea nitrogen/creatinine ratio increased
Renal dysfunction-related	10068447	Creatinine renal clearance abnormal
Renal dysfunction-related	10011372	Creatinine renal clearance decreased
Renal dysfunction-related	10018356	Glomerular filtration rate abnormal
Renal dysfunction-related	10018358	Glomerular filtration rate decreased
Renal dysfunction-related	10030302	Oliguria
Renal dysfunction-related	10072370	Prerenal failure
Renal dysfunction-related	10038435	Renal failure
Renal dysfunction-related	10061480	Renal function test abnormal
Renal dysfunction-related	10062237	Renal impairment
Metabolic acidosis	10027417	Metabolic acidosis
Hypoglycemia-related	10005554	Blood glucose abnormal
Hypoglycemia-related	10005555	Blood glucose decreased
Hypoglycemia-related	10020993	Hypoglycaemia
Hypoglycemia-related	10021000	Hypoglycaemic coma
Hypoglycemia-related	10021002	Hypoglycaemic encephalopathy
Hypoglycemia-related	10048803	Hypoglycaemic seizure
Hypoglycemia-related	10040576	Shock hypoglycaemic
Cognitive dysfunction-related	10057668	Cognitive disorder
Cognitive dysfunction-related	10010305	Confusional state
Cognitive dysfunction-related	10013395	Disorientation
Cognitive dysfunction-related	10027175	Memory impairment
Cognitive dysfunction-related	10048294	Mental status changes
Cognitive dysfunction-related	10001949	Amnesia
Elevated uric acid-related	10005861	Blood uric acid increased
Elevated uric acid-related	10020903	Hyperuricaemia

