CT-8.18-9	Incidence of IMP-related TEAEs by MedDRA System Organ Class and Preferred Term by Baseline Statin Medication (Safety Analysis Set)
CT-8.19	Incidence of AESIs by MedDRA System Organ Class and Preferred Term by eGFR (Safety Analysis Set)
CT-8.20	Incidence of IMP-related AESIs by MedDRA System Organ Class and Preferred Term by eGFR (Safety Analysis Set)
CT-9.1	Listing of Deaths (Safety Analysis Set)

- CT-9.2 Listing of Serious Adverse Events Other Than Death (Safety Analysis Set)
- CT-9.3 Listing of Discontinuations Due to Adverse Events (Safety Analysis Set)
- CT-10.1.1-1 Descriptive Statistics for Clinical Laboratory Test Results - Serum Chemistry (Safety Analysis Set)
- CT-10.1.1-2 Descriptive Statistics for Clinical Laboratory Test Results by Statin Response - Serum Chemistry (Safety Analysis Set)
- CT-10.1.2-1 Descriptive Statistics for Clinical Laboratory Test Results - Hematology (Safety Analysis Set)
- CT-10.1.2-2 Descriptive Statistics for Clinical Laboratory Test Results by Statin Response - Hematology (Safety Analysis Set)
- CT-10.1.3-1 Descriptive Statistics for Clinical Laboratory Test Results - Urinalysis (Safety Analysis Set)
- CT-10.1.3-2 Descriptive Statistics for Clinical Laboratory Test Results by Statin Response - Urinalysis (Safety Analysis Set)
- CT-10.2.1-1 Shift Tables of Clinical Laboratory Test Results - Serum Chemistry (Safety Analysis Set)
- CT-10.2.1-2 Shift Tables of Clinical Laboratory Test Results by Statin Response - Serum Chemistry (Safety Analysis Set)
- CT-10.2.2-1 Shift Tables of Clinical Laboratory Test Results - Hematology (Safety Analysis Set)
- CT-10.2.2-2 Shift Tables of Clinical Laboratory Test Results by Statin Response - Hematology (Safety Analysis Set)
- CT-10.2.3-1 Shift Tables of Clinical Laboratory Test Results - Urinalysis (Safety Analysis Set)
- CT-10.2.3-2 Shift Tables of Clinical Laboratory Test Results by Statin Response - Urinalysis (Safety Analysis Set)
- CT-10.2.4-1 Shift Tables of Clinical Laboratory Test Results - Qualitative Urinalysis (Safety Analysis Set)
- CT-10.2.4-2 Shift Tables of Clinical Laboratory Test Results by Statin Response - Qualitative Urinalysis (Safety Analysis Set)

CT-10.3-1	Incidence of Potentially Clinically Significant Abnormalities in Laboratory Tests (Safety Analysis Set)
CT-10.3-2	Incidence of Potentially Clinically Significant Abnormalities in Laboratory Tests by Statin Response (Safety Analysis Set)

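### The creatinine flag is an absolute 2.0 mg/dL with no baseline-relative criterion and no on-treatment eGFR summary, so the all-data laboratory count has low sensitivity for creatinine rises in subjects who start below 1.0 mg/dL

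*SAP*

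**What the plan says.** SAP 9.3 plans three summaries that include creatinine.

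- For quantitative parameters, "descriptive statistics of the actual value and change from baseline will be calculated at each time point".
- Values are classed against the normal limits as below, within or above, and for these classes "shift tables at each time point from baseline will be prepared".
- The third summary is a count of flagged subjects, worded as "The number and percentage of subjects meeting the criteria for identifying laboratory values of potential clinical relevance". It is calculated from all on-treatment data, including unscheduled visits. The criteria are in Appendix 2, where the creatinine row is 2.0 mg/dL or more with no part relative to the subject's own baseline.

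The first two summaries follow the visit windows of SAP 3.4, which keep only the last value in each window.

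eGFR is an eligibility criterion (Protocol 5.2.2), a baseline characteristic (SAP 7.2) and a subgroup factor (SAP 8.3 and 9.2.2). Protocol Table 10.2-1 does not list it as a laboratory parameter, and no post-baseline summary of it is planned. Creatinine is in that table, and clinical laboratory tests are scheduled at every visit.

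Protocol 8.7.1 says that ETC-1002 was associated in trials outside Japan with several laboratory changes, "as well as creatinine and urea nitrogen increased, although these were not clinically significant", and asks that these values be watched closely. SAP Appendix 5 makes renal dysfunction an adverse event of special interest; "Blood creatinine increased" is one of its terms.

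**The concern.** Safety is the primary objective, and a creatinine rise is an effect the protocol already associates with the drug. The Appendix 2 count is the one creatinine summary that counts subjects and also uses every on-treatment value, so it is the natural place to look for individual rises. An absolute limit of 2.0 mg/dL demands a larger proportional rise the lower the subject starts. Without on-treatment eGFR, no second renal measure shows the course of kidney function. A low or zero count could then be quoted as renal reassurance although the criterion had little chance of being met by subjects with low starting values.

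**Working it through.** **Inputs.** The limit of 2.0 mg/dL is from SAP Appendix 2. It is stated without derivation, so there is no plan figure to reproduce. The documents give neither a distribution of baseline creatinine nor an upper limit of normal (ULN). I assume baselines of 0.6 to 1.2 mg/dL and a ULN of 0.8 to 1.2 mg/dL.

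**Step 1: rise needed to be counted.** Fold rise = 2.0 / baseline.

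| Baseline (mg/dL) | Fold rise to reach 2.0 | Value after doubling | Counted? |
|---|---|---|---|
| 0.6 | 3.33 | 1.2 | no |
| 0.7 | 2.86 | 1.4 | no |
| 0.8 | 2.50 | 1.6 | no |
| 0.9 | 2.22 | 1.8 | no |
| 1.0 | 2.00 | 2.0 | yes |
| 1.2 | 1.67 | 2.4 | yes |

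A doubling is missed when 2 × baseline < 2.0, that is, when baseline is below 1.0 mg/dL. A rise from 0.7 to 1.9 mg/dL (1.9/0.7 − 1 = +171%) is not counted.

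**Step 2: does the shift table pick up what Step 1 misses?** From a baseline within range, a doubling stays within range when 2 × baseline ≤ ULN, that is, baseline ≤ ULN/2. For a ULN of 0.8 to 1.2 this means a baseline of at most 0.4 to 0.6 mg/dL. From a higher within-range baseline, the doubled value moves from within to above. The rise from 0.7 to 1.9 does so at any ULN in the assumed range.

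Three limits remain:
- The table does not separate a value just over the ULN from a doubling.
- A subject already above range shows no shift. With a ULN of 0.8, a rise from 0.9 to 1.8 stays in the above category and also stays under 2.0.
- Only the last value in the window is used, so a peak followed by a lower repeat in the same window drops out.

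**Step 3: the other displays.** SAP 7.2 defines descriptive statistics to include the minimum and maximum. The largest change at each visit is therefore shown, again from the last value per window and without the number of subjects above any given size. Listings CT-10.4 and LAB-1.2 show values but give no counts. A laboratory value enters the special-interest table only if reported as an adverse event. Under Protocol 8.8.1 that follows investigator judgement, or the value leading to discontinuation or meeting a seriousness criterion.

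**Step 4: effect of a relative row.** At 1.5 × baseline, the flag would sit at 0.9 mg/dL from 0.6, 1.2 from 0.8, 1.5 from 1.0 and 1.8 from 1.2. From 2.0/1.5 = 1.33 mg/dL upward, the existing row is reached first or at the same value.

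**The case against.** The strongest reply is that the rise is displayed several times over: shift tables, by-visit extremes, listings, renal adverse event terms and a separate urea nitrogen row in Appendix 2. That stands. A reader might infer that a subject with normal renal function can double creatinine and be counted nowhere, or that the trial cannot detect the effect outside existing renal impairment. The documents support neither. Under the assumed ULN most doublings from a within-range baseline are counted in the shift table, and Appendix 2 itself flags a 2.5-fold rise from 0.8 mg/dL.

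A second reply is that an absolute or ULN-based limit is the norm in Appendix 2. This also stands. Hematocrit carries a change part ("percentage points decrease from baseline"), as do vital signs and ECG in Appendices 1 and 3, but there the change is required in addition to an absolute limit. It narrows those rules and sets no precedent for a stand-alone relative trigger. Only weight and urine protein and glucose are judged on change alone.

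Third, the protocol calls the earlier increases not clinically significant, and it supplies no multiple of baseline. Both are true. The first is a reason for moderation, but a 52-week safety trial should be able to test that statement in its own population. The second means that any multiple must be declared as a choice.

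What these replies leave open is narrow: no planned table counts subjects by the size of their creatinine rise, and the all-data count uses a criterion that low starters seldom approach.

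**Conclusion.** The point holds as a matter of sensitivity. A subject with baseline creatinine below 1.0 mg/dL can at least double without being counted as potentially clinically relevant, in the only creatinine count that uses all on-treatment values. No on-treatment eGFR summary makes up for this. The threshold arithmetic rests only on the 2.0 mg/dL limit. The statement that most doublings reach the shift table rests on the assumed ULN of 0.8 to 1.2 mg/dL. The number of subjects who would be reclassified is unknown, because the documents give no baseline distribution. The planned safety analysis is not invalid, and a zero count would not stand alone. This is an inexpensive improvement to a descriptive plan whose primary objective is safety.

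**What to change.** Analysis only, with no new samples or visits:

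- Keep the 2.0 mg/dL creatinine row in Appendix 2.
- Add one prespecified row relative to baseline, applied to any post-dose value including unscheduled visits, for example creatinine of at least 1.5 × baseline. State that the multiple is a choice.
- Add eGFR to the by-visit actual-value and change tables in SAP 9.3. State the formula, which the documents do not give, and use the same one as for baseline eGFR.
- State that the relative row is read mainly in newly enrolled subjects, whom the SAP already tabulates separately. Baseline is the last value before the first dose in this trial, and for rollover subjects the Day 1 results are those of Week 12 of the confirmatory trial. Anyone given ETC-1002 there has an on-drug baseline, and an early rise would already be in it.

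The cost is one extra row and one derived parameter. The relative row may also flag small absolute rises from low baselines: from 0.6 mg/dL, a rise of 0.3 mg/dL is enough. Retaining the absolute row beside it lets a reader separate the two.

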9.4 Vital Sign Data

For vital signs (blood pressure, pulse rate, and body temperature), descriptive statistics of the actual value and change from baseline will be calculated at each time point.

The number and percentage of subjects meeting the criteria for identifying vital signs of potential clinical relevance ([Appendix 1: Criteria for Identifying Vital Signs and Weight of Potential Clinical Relevance](#)) after IMP administration will be calculated. All data obtained after IMP administration during the treatment period will be analyzed, including those obtained at unscheduled visits.

9.5 Physical Examination Data

Physical findings will be presented in a listing of subjects.

9.6 Electrocardiogram Data

For ECG parameters (heart rate, PR interval, RR interval, QRS interval, QT interval, and QTcF), descriptive statistics of the actual value and change from baseline will be calculated at each visit (Weeks 12, 24, 36, and 52).

The number and percentage of subjects with an actual value of QTcF of >450 ms, >480 ms, or >500 ms at any postdose time point will be calculated. In addition, the number and percentage of subjects with a change from baseline in QTcF of >30 ms or >60 ms at any postdose time point will be calculated. All data obtained after IMP administration will be analyzed, including those obtained at unscheduled visits. Similarly, the number and percentage of subjects meeting these criteria at each postdose time point will also be calculated.

For assessment of normality/abnormality, shift tables at baseline and each time point will be prepared.

The number and percentage of subjects meeting the criteria for identifying ECG measurements of potential clinical relevance ([Appendix 3: Criteria for Identifying ECG Measurements of Potential Clinical Relevance](#)) after IMP administration will be calculated. All data obtained after IMP administration will be analyzed, including those obtained at unscheduled visits.

9.7 Other Safety Data

9.7.1 Body Weight

For body weight, descriptive statistics of the actual value and change from baseline will be calculated at each visit (Weeks 4, 12, 20, 24, 28, 36, 44, and 52).

The number and percentage of subjects meeting the criteria for identifying body weight of potential clinical relevance ([Appendix 1: Criteria for Identifying Vital Signs and Weight of Potential Clinical Relevance](#)) after IMP administration will be calculated. All data obtained after IMP administration will be analyzed, including those obtained at unscheduled visits.

10 Pharmacokinetic Analyses

No pharmacokinetic analysis is planned.

11 Pharmacodynamic Analyses

No pharmacodynamic analysis is planned.

12 Pharmacogenomic Analyses

No pharmacogenomic analysis is planned.

13 Interim Analysis

No interim analysis is planned.

14 Changes in the Planned Analyses

Not applicable.

15 References

Not applicable.

Appendix 1 Criteria for Identifying Vital Signs and Weight of Potential Clinical Relevance

Variable	Criterion Value ^a	Change Relative to Baseline ^a
Pulse rate	>120 bpm	≥15 bpm increase
Pulse rate	<50 bpm	≥15 bpm decrease
Systolic blood pressure	>160 mmHg	≥20 mmHg increase
Systolic blood pressure	<90 mmHg	≥20 mmHg decrease
Diastolic blood pressure	>100 mmHg	≥15 mmHg increase
Diastolic blood pressure	<50 mmHg	≥15 mmHg decrease
Weight	N/A	≥7% increase
Weight	N/A	≥7% decrease

^aIn order to be identified as potentially clinically relevant, an on-treatment value must meet the “Criterion Value” and also represent a change from the subject’s baseline value of at least the magnitude shown in the “Change Relative to Baseline” column.

Appendix 2 Criteria for Identifying Laboratory Values of Potential Clinical Relevance

Laboratory Tests	Criteria
Chemistry	
AST	$\geq 3 \times$ upper limit of normal (ULN)
ALT	$\geq 3 \times$ ULN
Bilirubin, Total	$\geq 2 \times$ ULN
ALP	$\geq 3 \times$ ULN
Urea nitrogen	≥ 30 mg/dL
Creatinine	≥ 2.0 mg/dL
Creatine kinase (CK)	$\geq 4 \times$ ULN
Uric acid	≥ 9 mg/dL
Hematology	
Hematocrit	Males: $\leq 37\%$ and ≥ 3 percentage points decrease from baseline Females: $\leq 32\%$ and ≥ 3 percentage points decrease from baseline
Hemoglobin	Males: ≤ 11.5 g/dL Females: ≤ 9.5 g/dL
Leukocyte count	$\leq 2,800 \times 10^6/L$
Leukocyte count	$\geq 16,000 \times 10^6/L$
Platelet count	$\leq 7.5 \times 10^{10}/L$
Platelet count	$\geq 70 \times 10^{10}/L$
Urinalysis	
Protein	Increase of ≥ 2 units
Glucose	Increase of ≥ 2 units
Additional criteria	
Chloride	≤ 90 mEq/L
Chloride	≥ 118 mEq/L
Potassium	≤ 2.5 mEq/L
Potassium	≥ 6.5 mEq/L
Sodium	≤ 126 mEq/L
Sodium	≥ 156 mEq/L
Calcium	≤ 8.2 mg/dL
Calcium	≥ 12 mg/dL
Glucose	Fasting: ≥ 126 mg/dL Non-Fasting: ≥ 200 mg/dL
Glucose	≤ 50 mg/dL
Total cholesterol	≥ 240 mg/dL
LDL cholesterol	≥ 160 mg/dL
HDL cholesterol	< 40 mg/dL
Triglycerides, Fasting	≥ 150 mg/dL

Appendix 3 Criteria for Identifying ECG Measurements of Potential Clinical Relevance

Variable	Criterion Value^a	Change Relative to Baseline^a
Heart rate	≥ 120 bpm	increase of ≥ 15 bpm
Heart rate	≤ 50 bpm	decrease of ≥ 15 bpm
PR	≥ 200 ms	increase of ≥ 50 ms
QRS	≥ 120 ms	increase of ≥ 20 ms

^aIn order to be identified as potentially clinically relevant, an on-treatment value must meet the “Criterion Value” and also represent a change from the subject’s baseline value of at least the magnitude shown in the “Change Relative to Baseline” column.

Appendix 4 Preferred Terms for Statins and Ezetimibe

Drug	CRF Option for Drug Name (English)	Preferred Term WHODD Drug Name	Preferred Term WHODD Drug Code	WHODD Drug Code 6 digits
Statins	Pravastatin sodium	PRAVASTATIN SODIUM	00880402001	008804
	Simvastatin	SIMVASTATIN	00848101001	008481
	Rosuvastatin calcium	ROSUVASTATIN CALCIUM	01588602001	015886
	Pitavastatin calcium	PITAVASTATIN CALCIUM	06470002001	064700
	Atorvastatin calcium trihydrate	ATORVASTATIN CALCIUM TRIHYDRATE	01326106001	013261
	Fluvastatin sodium	FLUVASTATIN SODIUM	01224502001	012245
	Caduet No.1	AMLODIPINE BESILATE; ATORVASTATIN CALCIUM	12872303001	128723
	Caduet No.2	AMLODIPINE BESILATE; ATORVASTATIN CALCIUM	12872303001	128723
	Caduet No.3	AMLODIPINE BESILATE; ATORVASTATIN CALCIUM	12872303001	128723
	Caduet No.4	AMLODIPINE BESILATE; ATORVASTATIN CALCIUM	12872303001	128723
	Amaluet No.1	AMLODIPINE BESILATE; ATORVASTATIN CALCIUM TRIHYDRATE	12872304001	128723
	Amaluet No.2	AMLODIPINE BESILATE; ATORVASTATIN CALCIUM TRIHYDRATE	12872304001	128723
	Amaluet No.3	AMLODIPINE BESILATE; ATORVASTATIN CALCIUM TRIHYDRATE	12872304001	128723
	Amaluet No.4	AMLODIPINE BESILATE; ATORVASTATIN CALCIUM TRIHYDRATE	12872304001	128723
	Atozet LD	ATORVASTATIN CALCIUM; EZETIMIBE	12872002001	128720
	Atozet HD	ATORVASTATIN CALCIUM; EZETIMIBE	12872002001	128720
	Rosuzet LD	EZETIMIBE; ROSUVASTATIN CALCIUM	10641002001	106410
	Rosuzet HD	EZETIMIBE; ROSUVASTATIN CALCIUM	10641002001	106410
	Other	LIPID MODIFYING AGENTS, COMBINATIONS	90083401001	900834
Ezetimibe	Ezetimibe	EZETIMIBE	01587001001	015870
	Atozet LD	ATORVASTATIN CALCIUM; EZETIMIBE	12872002001	128720
	Atozet HD	ATORVASTATIN CALCIUM; EZETIMIBE	12872002001	128720
	Rosuzet LD	EZETIMIBE; ROSUVASTATIN CALCIUM	10641002001	106410
	Rosuzet HD	EZETIMIBE; ROSUVASTATIN CALCIUM	10641002001	106410
	Other	LIPID MODIFYING AGENTS, COMBINATIONS	90083401001	900834

